5.8.a. Aim 1 Evaluation Plan. Data for Aim 1 will come from the VA Corporate Data Warehouse (CDW) and other VA databases, such as the VA COVID-19 Shared Data Resource. Outcome data will include receipt of a COVID-19 vaccination (one or more doses of Pfizer, Moderna, Johnson and Johnson, or other WHO-authorized vaccine; completed primary series with two doses of Pfizer, Moderna, one dose of Johnson and Johnson, or the specified number of doses for other WHO-authorized vaccines) and receipt of the seasonal flu vaccine (exploratory hypothesis) during the one-year trial. Covariates will include baseline demographics (e.g., age, race/ethnicity, gender, service connection), clinical and mental health diagnoses, and medications and healthcare utilization in the year prior to the start of the trial (e.g., VA and non-VA primary care visits, inpatient hospitalizations). The primary data sources for VA-administered vaccines are the ORDCOVID Vaccine tables, which are enhancements of the CDW Immunization table and is updated weekly. Immunizations performed outside VHA for which the administration fees are reimbursed by VHA will be ascertained from CDW Community Care data in the Payment Integrity Tool (PIT) files and the Integrated Veteran Care Consolidated Data Set. which replaced PIT. Immunizations for which administration fees are reimbursed by Medicare will be ascertained from the Centers for Medicare and Medicaid Services (CMS) Institutional Outpatient, Carrier, and Medicare Advantage files using the guarterly and annual updates as they become available through the VA Information Resource Center (VIREC). Aggregate data for county vaccination rates for adults older and younger than 65, by week, are available from the CDC COVID Data Tracker dataset "COVID-19 Vaccinations in the United States, by County". (See Data Analysis section below for plan to ascertain vaccination status for Veterans who receive COVID-19 vaccination outside of VA in which vaccination data is not accessible to VA researchers.)

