We will use the Bayesian multiple imputation model described in the main analysis for the secondary outcome for the same motivations described therein. Due to the uncertainty in the definition of the eligibility, that is, knowing with 100% certainty that a Veteran did not complete the vaccine primary series prior to study start, the total count of eligible Veterans at each clinic (i.e., the denominator) will be reduced by a random quantity to represent the count of Veterans who were misclassified as having not completed the primary series at or before baseline. Thereafter, we will correct the count of observed primary series completions by adding a random value to represent the unknown primary series completions over the course of the

study that, if ignored, would be labeled as incomplete primary series in the eligible sample. Analytical summaries will be identical to those laid out in the main analysis.

Analysis of Exploratory Outcomes

No control for multiplicity will be performed for exploratory outcomes. We will use the same methods proposed to analyze the primary and secondary outcomes to analyze receipt of a booster vaccination and flu vaccination. We will adapt methods presented by Sinclair et al. (2012) to estimate the spill-over effect of the intervention by analyzing receipt of seasonal flu vaccination. CDC guidelines on the minimum length of time between COVID-19 primary series completion and booster eligibility decreased during the study period. We will use the most recent guideline in effect during our study period, which was a minimum of 60 days from primary series completion to receipt of the first booster. In instances where a third mRNA vaccine dose was administered prior to 60-days following the second mRNA dose, that is classified as an additional primary series dose per CDC guidelines for Veterans with immunosuppression, and the date of that vaccination is defined as the date of primary series completion. Due to difficulties ascertaining which Veterans have immunosuppression, and the relatively loose guidelines for which conditions qualify, third doses have been defined empirically based on vaccination dates.

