6.1.1 Primary Outcome

6.1.1.1. Original Design Assumptions

Of the 16 VAHCS in VHA region 16 and 21, 10 VAHCS agreed to participate in the study, with an average of 9 to 10 clinics per VAHCS, and an average of at least 1,000 Veterans per clinic. These numbers were based on conservative projections of the number of Veterans at the time of randomization and account for missing vaccination (i.e., misclassification) status for Veterans who may have been vaccinated outside of the VA. We hypothesize that the larger proportion of Veterans will get vaccinated (both first and fully) within 12 months in the VAI arm compared to usual care. Calculations were conducted with PASS 19 (Kaysville, Utah) using sample size for mixed models for two sample proportions with a 3-level hierarchical design assuming an intra-cluster correlation (ICC) of 0.07 for individuals within a clinic and an ICC of 0.02 for clinics within a VAHCS [Elley CR, et al. (2005)]. With a type I error rate of 0.05 (two-sided) we will have at least 90% power to detect between a 9.6% and 14.6% difference in vaccination rates assuming a rate in the usual care group ranging from 5% to 20% and a total sample size of 90,000 to 100,000. **Table 1** shows details of different scenarios.

Table 1: Detectable difference for comparing 2 proportions in a hierarchical model assuming 5 VAHCS per arm with on average 9-10 clinics per VAHCS and on average 1000 individuals per clinic, 90% power, type I error of 5% (two-sided) and level 1 ICC of 0.07 and level 2 ICC of 0.02

Total Sample Size	Clinics VAMC*	Rate in Usual	Detectable
		Care	difference
90,000	9	5%	9.7%
100,000	10	5%	9.6%
90,000	9	10%	12.0%
100,000	10	10%	11.8%
90,000	9	15%	13.5%
100,000	10	15%	13.3%
90,000	9	20%	14.6%
100,000	10	20%	14.4%

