9.1.1 General Approach

Analyses will be based on the intent to treat principle, that is any Veteran at the start of the trial who receives VHA primary care services at a participating site within one year of the study start date (Aim 1) will be considered in the denominator of the vaccination rate regardless of whether they received the intervention. Randomization was stratified by VISN and constrained based on baseline vaccination rate; therefore, all analyses will adjust for VISN and baseline vaccination rate. Since randomization was conducted at the site level, but analyses will include individual level data, we will assess the adequacy of the randomization by comparing baseline characteristics of participants between the two groups. No statistical tests will be used to assess these comparisons. Variables will be summarized using descriptive statistics. Nominal and ordinal categorical variables will be summarized using frequencies and percentages. Continuous variables will be summarized with the following descriptive statistics: N, mean, standard deviation, median, minimum, maximum, interquartile range, and range. We will also use plots (e.g., box and whisker) to explore the distribution of the data. Both the primary and secondary outcome will be tested with an alpha of 0.05 (two-sided). All other outcomes will be considered exploratory and will not be subject to corrections for multiple testing.

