9.1.3 Background of Vaccination Records Ascertainment

The uncertainty in vaccine records ascertainment is pertinent to discuss prior to describing how we will analyze the primary, secondary, and exploratory outcomes with standard and sensitivity analyses. There will be Veterans who receive their COVID-19 vaccinations outside of the VA system or from venues not currently captured in VA databases (i.e., State fairs, shopping malls etc.). This could inflate our denominator of unvaccinated Veterans at the start of the trial (i.e., false negatives – Veterans are actually vaccinated). It could also decrease our numerator during the trial because we could miss Veterans who received COVID-19 vaccines during the study follow-up period at non-VA sites not captured in VA data. There are two main avenues to supplement missing vaccine information in VA records; however, both have important limitations.

First, we will supplement VA vaccination records with Medicare claims data. While the federal government paid for the vaccine product, providers were permitted to bill for the cost of administering the vaccines. Based on analyses from the VA Information Resource Center (VIReC) in 2021, linking Medicare data substantially improved ascertainment. There are a few limitations. First, due to a lag, claims data will not be available for the complete study period. For Veterans enrolled in traditional Medicare fee-for-service, which account for approximately 70% of Medicare-enrolled Veterans, we anticipate data being available through 2022 [Centers for Medicare and Medicaid Services (2021)]. For Veterans enrolled in Medicare Advantage (i.e., managed care programs), data will only be available through 2021. Second, during the early phases of vaccine rollout in 2021 when mass vaccination clinics had been common, Centers for Medicare and Medicaid Services estimated that claims were never submitted for as many as half of Medicare-age people.

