9.1.5.2 Missing Outcomes/Misclassification of Vaccination Status

We will use the Bayesian multiple imputation model described in Section 9.1.4.3 for the secondary outcome for the same motivations described therein. Due to the uncertainty in the definition of the eligibility, that is, knowing with 100% certainty that a Veteran did not complete the vaccine primary series prior to study start, the total count of eligible Veterans at each clinic (i.e., the denominator) will be reduced by a *random* quantity to represent the count of Veterans who were misclassified as having not completed the primary series at or before baseline. Thereafter, we will correct the count of observed primary series completions by adding a *random* value to represent the unknown primary series completions over the course of the study that, if ignored, would be labeled as incomplete primary series in the eligible sample. Analytical summaries will be identical to those laid out in Section 9.1.4.2.

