9.1.6 Analysis of Exploratory Outcomes

No control for multiplicity will be performed for exploratory outcomes. We will use the same methods proposed to analyze the primary and secondary outcomes to analyze receipt of a booster vaccination and flu vaccination. We will adapt methods presented by Sinclair et al. (2012) to estimate the spill-over effect of the intervention by analyzing receipt of seasonal flu vaccination. CDC guidelines on the minimum length of time between COVID-19 primary series completion and booster eligibility decreased during the study period. We will use the most recent guideline in effect during our study period, which was a minimum of 60 days from primary series completion to receipt of the first booster. In instances where a third mRNA vaccine dose was administered prior to 60-days following the second mRNA dose, that is classified as an additional primary series dose per CDC guidelines for Veterans with immunosuppression, and the date of that vaccination is defined as the date of primary series completion. Due to difficulties ascertaining which Veterans have immunosuppression, and the relatively loose guidelines for which conditions qualify, third doses have been defined empirically based on vaccination dates.

Because of evolving guidance on COVID vaccinations (products, dosing, etc.) in the context of fluctuating background COVID-19 prevalence at different VAHCS sites combined with seasonal flu vaccination in the Fall and Winter months, we expect temporal and site trends. Therefore, we plan to conduct the following exploratory analyses: (1) adjust for time-dependent variables; and (2) perform analyses stratified by time period and site.

9.2 Aim 2

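### The misclassification sensitivity analysis for series completion takes already-vaccinated Veterans out of the denominator but leaves their recorded completions in the numerator

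*SAP*

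**What the plan says.** The secondary outcome is primary series completion in Veterans recorded as unvaccinated (SAP 5.1.2), worded in SAP 9.1.5 as not having started or completed the series at randomization. Completion is a dose count. Protocol 5.8.a gives it as "completed primary series with two doses of Pfizer, Moderna, one dose of Johnson and Johnson", or the set number of doses for other authorized products.

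The main analysis uses VA electronic records only (SAP 9.1.3). That section accepts that Veterans vaccinated elsewhere may be missed, and names two consequences. One is at baseline: "This could inflate our denominator of unvaccinated Veterans at the start of the trial". The other is a numerator that is too low because outside doses during follow-up are missed.

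SAP 9.1.5.2 builds its correction on those two errors. The count of eligible Veterans at each clinic is first reduced by a random number who had in fact completed the series by baseline. The SAP then turns to the numerator: "we will correct the count of observed primary series completions by adding a" random value. Protocol 5.9 words the same step as "we will correct the count of observed primary series completions by adding a random value". Neither SAP 9.1.4.2, nor SAP 9.1.5.2, nor the matching text in Protocol 5.9 has a step that subtracts completions.

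**The concern.** A Veteran vaccinated elsewhere before the trial, with no VA record of it, enters the secondary analysis as unvaccinated. If that Veteran then receives two mRNA doses at VA within the 12 months, or one Janssen dose, the dose count reads as a completed primary series although the doses were boosters. This is a third kind of error, a false completion, and SAP 9.1.3 does not name it.

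The correction in 9.1.5.2 removes such Veterans from the denominator but keeps their events. A rate whose numerator includes people no longer in its denominator is inconsistent, and the error is upward. The arms are exposed to it unequally if the intervention raises booster uptake, which hypotheses H1a and H1d both anticipate. An analysis meant to show whether the secondary result survives misclassification could then add an apparent benefit of its own.

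**Working it through.** **Scale set by the plan.** SAP 6.1.2 applies the primary power calculation to the secondary outcome. Its inputs (SAP 6.1.1.1) are 5 systems per arm, 9 or 10 clinics each, 1,000 Veterans per clinic, ICCs of 0.07 and 0.02, two-sided alpha of 0.05 and 90% power.
- Design effect, 9 clinics: 1 + 999 × 0.07 + 1,000 × 8 × 0.02 = 230.93. Effective n per arm: 45,000 / 230.93 = 194.9.
- Design effect, 10 clinics: 1 + 999 × 0.07 + 1,000 × 9 × 0.02 = 250.93. Effective n per arm: 50,000 / 250.93 = 199.3.
- Solving the pooled two-proportion formula at usual-care rates of 5, 10, 15 and 20% gives 9.74/9.61, 11.97/11.82, 13.47/13.31 and 14.55/14.37 points. The SAP's Table 1 has 9.7/9.6, 12.0/11.8, 13.5/13.3 and 14.6/14.4. The table reproduces.

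**The correction.** At a clinic let N be Veterans listed as unvaccinated, M those of them already vaccinated, T true completions, F false completions recorded for the M, and A the missed completions added.
- Rate as 9.1.5.2 is written: (T + F + A) / (N − M).
- Consistent rate: (T + A) / (N − M).
- Excess, with A the same in both: F / (N − M). Writing f = M/N and g = F/M, this is f·g / (1 − f).

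If A is instead a rate r times the Veterans still labelled incomplete, leaving F in lowers A by r·F and the excess becomes (1 − r)·f·g / (1 − f). It shrinks but does not vanish. The figures below take A = 0.

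**Assumed values.** The documents give no f, no g and no true completion rate c. With c = 5%, the recorded rate is f·g + (1 − f)·c:

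| f | g | Recorded rate | False share of recorded completions | Rate under 9.1.5.2 | Excess over 5% |
|---|---|---|---|---|---|
| 0.1 | 0.02 | 4.7% | 4% | 5.2% | 0.2 points |
| 0.3 | 0.02 | 4.1% | 15% | 5.9% | 0.9 points |
| 0.3 | 0.05 | 5.0% | 30% | 7.1% | 2.1 points |
| 0.4 | 0.02 | 3.8% | 21% | 6.3% | 1.3 points |
| 0.5 | 0.10 | 7.5% | 67% | 15.0% | 10.0 points |

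Second row: 0.3 × 0.02 + 0.7 × 0.05 = 0.041; 0.006 / 0.041 = 15%; 0.041 / 0.7 = 5.9%. Removing F as well gives 0.035 / 0.7 = 5.0%, the true rate.

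**Arm difference with no true effect on completion.**
- g one point higher in the intervention arm, f = 0.3 in both: main secondary analysis 0.3 × 1 = 0.3 points; 9.1.5.2 gives 0.3 / 0.7 = 0.43 points. The correction enlarges the artefact by 1/(1 − f).
- Same change in g at f = 0.4: 0.4 and 0.4 / 0.6 = 0.67 points.
- g = 0.02 in both arms, f = 0.4 against 0.3: 9.1.5.2 gives 1.33 − 0.86 = 0.5 points.
- f and g equal in both arms: no difference; only the level of the rate is wrong.

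**Effect on the test.** At f = 0.3, recorded rates of 4.1% and 4.4% and effective n of 194.9, the standard error is √[(0.041 × 0.959 + 0.044 × 0.956) / 194.9] = 0.0204. The shift is 0.003 / 0.0204 = 0.147 standard errors, and the two-sided rejection rate moves from 5.0% to about 5.2%. This uses planned, not actual, cluster sizes.

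**The case against.** The strongest reply concerns reach. The one-sided correction sits in a sensitivity analysis of a secondary outcome. The main secondary estimate makes no denominator correction, and its artefact is small against differences of 9.6 to 14.6 points that the plan is sized to detect. That stands. A reader might infer that the tested secondary result is exposed to a material false positive; the arithmetic above does not support it.

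The event is also narrow. For a Veteran with no recorded dose, one mRNA booster is not a completion; it takes two in the window, or one Janssen dose. Only if the wider wording of SAP 9.1.5 admits Veterans with one recorded dose would a single VA mRNA dose be enough. So g may well be low.

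A partial safeguard exists. SAP 9.1.5.1 repeats the analysis with Medicare/Medicaid and IZ Gateway records and keeps only Veterans not reported to have started or completed the series at randomization. A Veteran whose earlier doses are found leaves numerator and denominator together. It reaches only Veterans whose outside records can be found: the Gateway covers 9 of the 10 sites and queries a Veteran only when care is received, and Medicare claims are incomplete. It tests the mechanism in that group but does not repair 9.1.5.2.

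Two further inferences go beyond the documents:
- The protocol's flu project found 290 of 488 Veterans (59%) already vaccinated without a record. One might take this as a value for f. It concerned another vaccine, and the protocol itself calls the sample small, single-site and not generalizable.
- SAP 9.1.6 says "third doses have been defined empirically based on vaccination dates". One might conclude that all dose roles are inferred from dates. The rule covers only third mRNA doses in the booster analysis. The documents do not say how first and second doses are classed, or whether the VA tables hold a dose-number field that would screen boosters out.

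**Conclusion.** The concern holds for SAP 9.1.5.2 and the matching protocol text. As written, the correction overstates the completion rate by f·g/(1 − f) whenever false completions exist. That is 0.9 points at f = 0.3 and g = 0.02, and 0.2 to 10 points over the assumed range. The direction follows from the algebra; the size rests wholly on assumed values. Bias in the arm difference needs f or g to differ by arm. That is plausible because the intervention promotes any dose, including boosters, but no document shows it. The primary outcome is not affected by this step, because SAP 9.1.4.2 leaves its denominator uncorrected. The consequence is a sensitivity analysis that could mislead about robustness, not an invalid main result.

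**What to change.** In SAP 9.1.5.2 and the matching text of Protocol 5.9:
- When misclassified Veterans are drawn out of the denominator, also remove a modelled count of their recorded completions from the numerator, and only then add missed completions.
- Vary that false-completion rate over a stated range that includes zero and values that differ by arm.
- Extend SAP 9.1.3 to name false completions as a third error.
- Correct the reference to Section 9.1.4.3, which does not exist; the model is in 9.1.4.2.

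Do not also impose a date-interval rule on pairs of doses in the main analysis. It could miscode genuine late second doses, and together with the subtraction above it would correct the same error twice.

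The cost is a few sentences of SAP and protocol text and a small change to the imputation code. The downside is one more investigator-set rate in a sensitivity analysis that already relies on such rates, so results should be shown across the range and not at a single value.

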9.1.6 Analysis of Exploratory Outcomes

No control for multiplicity will be performed for exploratory outcomes. We will use the same methods proposed to analyze the primary and secondary outcomes to analyze receipt of a booster vaccination and flu vaccination. We will adapt methods presented by Sinclair et al. (2012) to estimate the spill-over effect of the intervention by analyzing receipt of seasonal flu vaccination. CDC guidelines on the minimum length of time between COVID-19 primary series completion and booster eligibility decreased during the study period. We will use the most recent guideline in effect during our study period, which was a minimum of 60 days from primary series completion to receipt of the first booster. In instances where a third mRNA vaccine dose was administered prior to 60-days following the second mRNA dose, that is classified as an additional primary series dose per CDC guidelines for Veterans with immunosuppression, and the date of that vaccination is defined as the date of primary series completion. Due to difficulties ascertaining which Veterans have immunosuppression, and the relatively loose guidelines for which conditions qualify, third doses have been defined empirically based on vaccination dates.

Because of evolving guidance on COVID vaccinations (products, dosing, etc.) in the context of fluctuating background COVID-19 prevalence at different VAHCS sites combined with seasonal flu vaccination in the Fall and Winter months, we expect temporal and site trends. Therefore, we plan to conduct the following exploratory analyses: (1) adjust for time-dependent variables; and (2) perform analyses stratified by time period and site.

9.2 Aim 2

9.2.1 General Approach

We will use descriptive statistics--nominal and ordinal categorical variables will be summarized using frequencies and percentages while continuous variables will be summarized with the following descriptive statistics: N, mean, standard deviation, median, minimum, maximum, interquartile range, and range, to describe the populations surveyed.

9.2.1 Survey Data

Aim 2's primary outcome is receipt of vaccination, and we will explore characteristics that may be associated with the decision to receive the vaccine. This case-control design will use generalized linear mixed models that account for clustering by VAHCS to model vaccine receipt and estimate differences between those who were and were not vaccinated. We will present estimates and 95% confidence intervals.

